Over the entire study, a total of 20 SAEs were reported by 19 subjects. Of these 20 SAEs, 12 SAEs were reported by 12 subjects in the core period and nine SAEs were reported by 7 subjects during the extension period. More subjects in the 60 mg/d dose group (10.1%) experienced an SAE compared to the placebo to 30 mg/d (5.8%), placebo to 60 mg/d (3.9%), and 30 mg/d (4.2%) dose groups. Overall the most commonly reported SOCs for the SAEs were in Gastrointestinal Disorders and Injury, Poisoning and Procedural Complications categories. All of the SAEs were considered by the Investigators to be unlikely related or not related to study drug. Eight of the SAEs were considered by the Investigator to be severe or life threatening. No deaths occurred during the study.

A total of 9 subjects discontinued from the study due to a TEAE; two of these subjects had TEAEs that were considered to be treatment-related; hepatic steatosis in the 30 mg/d group and hepatotoxicity in the 60 mg/d group.

The safety of MN-166 from 30 to 80 mg/d has also been evaluated in single and multiple doses up to 14 days has also been evaluated in healthy volunteers and diabetes mellitus Type 1 & 2 patients and chronic pain patients (diabetic neuropathy and complex regional pain syndrome). MN-166 100 mg/d has been evaluated in single and multiple doses for up to 8 days (following 6 days of dose-incremental 40, 60 and 80 mg/d dosing at 2 days each) in healthy volunteers and diabetes mellitus Type 1 and 2 patients. A Phase 1b safety study to evaluate MN-166 in methamphetamine-dependent addicts recently completed enrollment. In this study, subjects received 40 mg/d for 1 week and then 100 mg/d for 1 week. Medication overuse headache (MOH) pain patients are currently being enrolled in a trial with dosing at 80 mg/d for 2 months and opioid addicts at 100 mg/d for 3 weeks in another trial. To date, approximately 450 subjects have been dosed with MN-166.

The Phase 2 RRMS trial results suggest that MN-166 is best positioned for primary neuroprotection in MS subjects (Fox 2010) and the dose-response data from this and other controlled neurological trials suggest that doses ≥ 60 mg/d may be ideal.

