
Reference Therapy, Dosage, and Mode of Administration: Matching-placebo capsules administered orally, twice a day in the morning and evening.

Criteria for Evaluation
 
Primary Safety Endpoints:
 
The proportion of subjects in each group with:
 
 Treatment-emergent adverse events (TEAEs) Treatment-emergent serious adverse events (TESAEs) 
Primary Tolerability Endpoints:
 
The proportion of subjects in each group who:
 
 Discontinue treatment early (early study termination and/or early study drug withdrawal) due to treatment-related AEs or SAEs Discontinue treatment early (early study termination and/or early study drug withdrawal) for any reason 
Primary Activity Endpoint:

Covariate-adjusted mean rate of change in brain atrophy over 96 weeks as measured by brain parenchymal fraction (BPF).

Major Secondary Activity Endpoints:

The secondary endpoints will be measured at 96 weeks by:

- Diffusion tensor imaging (DTI) in descending pyramidal white matter tracts
- Magnetization transfer ratio (MTR) imaging in normal-appearing brain tissue
- Retinal nerve fiber layer as measured by optical coherence tomography (OCT)
- Cortical atrophy as measured by cortical longitudinal atrophy detection algorithm [CLADA]

Additional secondary endpoints to be measured at 96 weeks are:

- Inflammatory disease activity, as measured by T1 lesion volume, T2 lesion volume, and annualized relapse rate
- Disability, as measured by Expanded Disability Status Scale (EDSS) and Multiple Sclerosis Functional Composite (MSFC)
- Quality of Life, as measured by Multiple Sclerosis Impact Scale (MSIS-29), EuroQol 5 Dimensions (EQ-5D), and Short Form-36 Health Survey (SF-36)
- Cognitive impairment, as measured by Symbol Digit Modalities Test and the Selective Reminding Test
- Neuropathic pain, as measured by Brief Pain Inventory (BPI).

Tertiary and Exploratory Endpoints: *see Objectives above.*

Pharmacokinetic: Plasma samples for analysis of ibudilast and its metabolite, 6,7-dihydrodiol (DHD), will be collected and population PK analysis will be performed.

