$$[a_{ih} \ b_{ih}]^T \sim \mathcal{N}(\mathbf{0}, \mathbf{G}), [a_h \ b_h \ c_h \ d_h]^T \sim \mathcal{N}(\mathbf{0}, \mathbf{H}), \epsilon_{ij} \sim \mathcal{N}(0, \sigma^2 \mathbf{I}_i), \text{ and } [a_i \ b_i]^T \perp [a_h \ b_h \ c_h \ d_h]^T \perp \epsilon_{ij}.$$

If individual site variance components in \mathbf{H} are negligible, then the associated random effects will be omitted to simplify the model. In the case that all \mathbf{H} components are negligible, we will revert to Equation (1) for the analysis.

Primary Objective #2: To evaluate the safety and tolerability of ibudilast versus placebo.

The main assessment of safety will involve a comparison of treatment-related SAEs across the two treatment groups. This will be assessed in two ways. First, the percentage of subjects who experience any treatment-related SAE in each group will be compared using a chi-square test. Then, the rates of treatment-related SAEs in each group will be compared using a Poisson regression model. We will also assess the values of laboratory assessments over time across the two groups using a LMM. To assess tolerability, the percentage of subjects who complete the entire treatment period will be compared across the two groups using a chi-square test. Appropriate constraints for baseline imbalance will be used in all statistical models.

Major Secondary Objectives: *To evaluate the activity of ibudilast at two years versus placebo, as measured by:*

- (1) *Diffusion tensor imaging (DTI) in descending pyramidal white matter tracts*
- (2) *Magnetization transfer ratio (MTR) imaging in normal-appearing brain tissue*
- (3) *Retinal nerve fiber thickness as measured by optical coherence tomography (OCT)*
- (4) *Cortical atrophy as measured by cortical longitudinal atrophy detection algorithm (CLADA)*

The secondary objectives will be analyzed using a model similar to that described above for the assessment of BPF. An exception is the OCT analysis will require additional random effects for eyes nested within patients. Additional details are provided below. The baseline intercepts will again be constrained to be equal to account for baseline imbalance.

Other Objectives

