2.2. Safety

The primary assessment of safety will compare the percentage of subjects in each group with:

- Treatment-emergent adverse events (TEAEs)
- Treatment-emergent serious adverse events (TESAEs)

For the purposes of this study, a treatment-emergent adverse event (AE) is any untoward medical occurrence in a study subject who was administered a medicinal (investigational) product and which does not necessarily have a causal relationship with this treatment. An AE can therefore be any unfavorable and unintended sign (including a significant abnormal laboratory finding), symptom, or disease temporally associated with the use of a medicinal (investigational) product, whether or not considered related to the medicinal (investigational) product. Adverse events may include the onset of a new illness and the exacerbation of pre-existing conditions. Other untoward events occurring in the framework of a clinical study are also to be recorded as AEs (e.g., those occurring during treatment-free periods, including screening or post-treatment follow-up periods), in association with study-related procedures and assessments or under placebo.

One of the following categories should be selected based on medical judgment, considering the definitions below and all contributing factors:

- **Related**: A clinical event, including laboratory test abnormality, occurs in a plausible time relationship to treatment administration, and which cannot be explained by concurrent disease or other medications or chemicals. The response to withdrawal of the treatment (de-challenge) should be clinically plausible. The event must be definitive pharmacologically or phenomenologically, using a satisfactory re-challenge procedure if necessary.
- **Probably Related**: A clinical event, including laboratory test abnormality, occurs within a reasonable time sequence to administration of the treatment, unlikely to be attributed to concurrent disease or other medications or chemicals, and which follows a clinically reasonable response on withdrawal (dechallenge). Re-challenge information is not required to fulfill this definition.
- **Possibly Related**: A clinical event, including laboratory test abnormality, occurs within a reasonable time sequence to administration of the treatment, but which could also be explained by concurrent disease or other medications or chemicals. Information on treatment withdrawal may be lacking or unclear.

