2.3. Tolerability

The primary assessment of tolerability will compare the percentage of subjects in each group who:

- Discontinue treatment early (early study termination and/or early study drug withdrawal) due to treatment-emergent AEs or SAEs
- Discontinue treatment early (early study termination and/or early study drug withdrawal) for any reason

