6. ANALYSIS POPULATIONS

Due to the exploratory nature of this study, all analyses to address the primary and major secondary objectives will be conducted at the 0.10 significance level. The analysis population of interest will differ depending on the objectives of any particular analysis.

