7.2.1 Safety

The primary assessment of safety will compare the percentage of subjects in each group with:

- Treatment-emergent adverse events (TEAEs)
- Treatment-emergent serious adverse events (TESAEs)

The main assessment of safety and tolerability will involve a comparison of treatment-related AEs and SAEs across the two treatment groups. First, the percentage of subjects who experience any treatment-related AE in each group will be compared using the following logistic regression model:

$$\text{logit}(Y_i) = \beta_0 + \beta_1 x_{1i} + \beta_2 x_{2i} + \beta_3 x_{3i} + \epsilon_i$$

where

- Y_i represents an indicator of whether or not i^{th} subject had at least one treatment related AE.
- $x_{1i} = 1$ if i^{th} subject was thought to be receiving immunomodulation therapy at randomization (IFN/GA), and 0 if the subject was not thought to be receiving immunomodulation therapy
- $x_{2i} = 1$ if i^{th} subject was thought to have primary progressive MS at randomization, and 0 if the subject was thought to have secondary progressive MS
- $x_{3i} = 1$ if i^{th} subject was randomized to the Ibudilast group, and 0 if the subject was randomized to placebo group
- ϵ_i is random error for the i^{th} subject

To determine if the percentage of subjects having any treatment related AEs differ across treatment group we will test the following hypothesis:

$$H_0: \beta_3 = 0 \text{ vs. } H_A: \beta_3 \neq 0$$

If the null hypothesis is rejected, and $\beta_3 > 0$, we will conclude that Ibudilast was responsible for a significantly greater frequency of treatment-related AEs. Similarly, if $\beta_3 < 0$, we will conclude that Ibudilast was responsible for a significantly lower frequency of treatment-related AEs. In addition to an overall comparison, this hypothesis will be repeated for assessing the percentage of subjects having at least one treatment-related AE within each MedDRA system organ class (SOC). If there are significant differences between groups within any specific SOC, then additional tests will compare differences across groups for specific MedDRA preferred terms in order to further explore the cause of the observed differences.

In addition to the comparison of percentages in the manner described above, the rates of treatment-related AEs in each group will be compared using the following Poisson regression model:

$$\log\left(\frac{Y_i}{T_i}\right) = \beta_0 + \beta_1 x_{1i} + \beta_2 x_{2i} + \beta_3 x_{3i} + \epsilon_i$$

where

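### Protocol and SAP name three different main safety comparisons for Primary Objective #2, and the one on treatment-related SAEs may be too sparse for the planned model's Wald test

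*Combined protocol and SAP*

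**What the plan says.** The endpoint is stated consistently. The protocol synopsis (Primary Safety Endpoints), protocol 11.1 and SAP 2.2 all use the proportion of subjects with TEAEs and with TESAEs. SAP 2.2 introduces them with "The primary assessment of safety will compare the percentage of subjects in each group with", and its AE definition applies regardless of suspected cause.

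The analysis is not consistent with that endpoint, or between documents:

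- SAP 7.2.1 repeats the endpoint, then continues: "The main assessment of safety and tolerability will involve a comparison of treatment-related AEs and SAEs across the two treatment groups". SAP 2.2 also puts primary interest on treatment-related AEs, meaning at least possibly related.
- Protocol 12.1.2, Primary Objective #2, says: "The main assessment of safety will involve a comparison of treatment-related SAEs across the two treatment groups". It uses a chi-square test and a Poisson model.
- All-causality TEAEs and TESAEs come at the end of SAP 7.2.1, as additional analyses to be done in a similar way.
- Early discontinuation counts as a tolerability endpoint if it is "due to treatment-related AEs or SAEs" in the protocol synopsis, but "due to treatment-emergent AEs or SAEs" in SAP 2.3 and 7.2.2.
- SAP 7.2.1 introduces its Poisson model for rates of treatment-related AEs, defines the outcome as the number of treatment-related SAEs, and interprets the coefficient in terms of AEs again.

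On the earlier phase 2 MS trial, the protocol synopsis reports: "All of the SAEs were considered by the Investigators to be unlikely related or not related to study drug".

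**The concern.** Safety and tolerability form one of two primary objectives, and a reader cannot tell which comparison answers it. The candidates can give different answers. In the earlier trial SAEs occurred in 10.1% of the 60 mg/d group and in 3.9% to 5.8% of the other groups, yet none would count as treatment-related under the SAP definition. A main test on related SAEs would have shown nothing there, while the all-causality comparison would have shown the difference. If the choice is left open until the data are unblinded, it becomes a post hoc choice on a primary objective.

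The SAP's main model for these events is logistic regression, with no method named for few or no events. The related-SAE comparison is where that is most likely to matter.

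**Working it through.** **1. The plan's own safety figure.** SAP 9.2 states at least 80% power for a 15-point difference at significance level 0.10, without a base rate. I used 125 per arm (SAP 1) and a two-sided test (the alternative in SAP 7.2.1), with power = Φ[(d − 1.645·s0)/s1].

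For 10% vs 25%: s0 = √(2 × 0.175 × 0.825/125) = 0.0481; s1 = √((0.10 × 0.90 + 0.25 × 0.75)/125) = 0.0471; power = Φ[(0.15 − 0.0791)/0.0471] = Φ(1.51) = 93.4%.

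Other base rates give 97.7% (5% vs 20%), 81.6% (25% vs 40%) and a minimum of 76.9% (42.5% vs 57.5%). The figure holds when the lower rate is at most 28% or at least 57%, so it reproduces at the low rates relevant to SAEs. It concerns a 15-point gap, however, and the SAE gaps seen before were 4.3 to 6.2 points.

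**2. All-causality SAE comparison.** Inputs: 125 per arm; "all analyses to address the primary and major secondary objectives will be conducted at the 0.10 significance level"; the earlier trial's percentages as an assumption. Power is the sum of Bin(a; 125, p1) × Bin(b; 125, p2) over all tables with an uncorrected chi-square of at least 2.706.

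| Assumed rates | Expected subjects per 125 | Exact power |
|---|---|---|
| 10.1% vs 3.9% | 12.6 vs 4.9 | 64% |
| 10.1% vs 4.2% | 12.6 vs 5.3 | 59% |
| 10.1% vs 5.8% | 12.6 vs 7.3 | 36% |

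None of the comparators is a pure placebo rate: 4.2% is the 30 mg/d arm, and 3.9% and 5.8% are placebo-to-active sequences counted over the whole study, including the open-label year. The four percentages and the 19 subjects with SAEs fit 10/99, 4/95, 3/52 and 2/51. On those inferred denominators the randomised placebo group is 5/103 (4.9%), which gives power of about 49%.

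**3. How sparse related SAEs could be.** With 0 related SAEs in 194 subjects randomised to active drug (table in protocol 4.5.1), the one-sided 95% upper limit is 1 − 0.05^(1/194) = 1.5%, or 125 × 0.0153 = 1.9 subjects per arm. Using only the 99 on 60 mg/d, it is 3.0%, or 3.7 subjects. The chance of no event in either arm, (1 − p1)^125 × (1 − p2)^125, is:

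- 53% at 0.5% vs 0%;
- 15% at 1.5% vs 0%;
- 8% at 1% vs 1%.

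Exact chi-square power at 1.5% vs 0% is about 29%.

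**4. What happens with one empty arm.** Take 3 events against 0:

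- Logistic Wald test, with two simulated binary covariates standing in for the strata: coefficient 20.8, standard error 11,576, p = 0.999. The true maximum-likelihood estimate is infinite.
- Likelihood-ratio test, unadjusted: G² = 2[3 ln(3/125) + 122 ln(122/125) − 3 ln(3/250) − 247 ln(247/250)] = 4.20, p = 0.041.
- Chi-square, uncorrected: 3.04, p = 0.081.
- Fisher exact: p = 0.247. Fisher needs 5 vs 0 (p = 0.060) to reach 0.10, because 4 vs 0 gives 0.122.

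The same data can fall on either side of 0.10 depending on the test, and SAP 7.2.1 does not say which is used. With 0 vs 0 no test is possible.

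**5. Treatment-related AEs.** Protocol 4.6.3 reports 26, 18 and 12 related TEAEs on 60 mg/d, 30 mg/d and placebo in the 12-month core period. That comparison will have data.

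**The case against.** The strongest reply is that nothing is lost. All TEAEs and TESAEs are to be modelled, SAP 7.2.1 still opens by calling them primary, and the Medical Safety Monitor receives quarterly tabulations of all AEs and SAEs by blinded group (SAP 10.3). Causality is judged blind and on the assumption of active treatment, so comparing related events is a valid randomised comparison. The interest in related AEs is stated openly in SAP 2.2, and protocol section 12 leaves the details to the SAP. This stands as far as it goes. All-causality events are demoted, not removed, and the issue is sensitivity and clarity, not bias. It does not settle which comparison is the main one.

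Three stronger readings are tempting, and the documents do not support them:

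- A reader might infer that the whole main safety assessment could be empty. Only the SAE half could be, because related AEs were not rare.
- A reader might infer that an empty arm makes the comparison untestable. Only the Wald test fails. SAP 7.2.1 states hypotheses without prescribing Wald, and likelihood-ratio and chi-square tests still work.
- A reader might infer that related SAEs will be zero, so that the test has no power. The zero comes from 30 to 60 mg/d in mainly relapsing-remitting patients with investigator attribution. This trial targets 100 mg/d in progressive MS, and the Medical Safety Monitor's judgement on SAEs overrides the site's (SAP 2.2).

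**Conclusion.** The point holds as an inconsistency over which analysis answers Primary Objective #2. Three main comparisons are named, and the stated endpoint is modelled only as an additional analysis. The tolerability definition differs between the protocol synopsis and the SAP, and the Poisson outcome contradicts its own introduction. These are matters of text and rest on no assumption.

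The size of the sparse-data risk is conditional. It is confined to treatment-related SAEs and rests on one synopsis sentence about a different population and lower doses. Power of 36% to 64% for all-causality SAEs assumes the earlier trial's percentages, which come from small counts. That comparison would be informative but still short of 80%; adopting it does not make the trial well powered for SAEs.

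The argument for putting all-causality events first is that they are the declared endpoint and that randomisation already supplies the causal comparison.

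**What to change.** - In SAP 7.2.1 and protocol 12.1.2, make the percentages with any TEAE and any TESAE the main comparison, and describe treatment-related AEs and SAEs as supportive. Align the primary-interest sentence in SAP 2.2.
- In SAP 7.2.1, name one test for sparse counts (exact, likelihood-ratio or Firth-penalised logistic) and the event count at which it replaces the standard one. State that 0 vs 0 will be reported descriptively.
- Use treatment-emergent in both tolerability definitions (protocol synopsis, SAP 2.3 and 7.2.2).
- Correct the Poisson outcome in SAP 7.2.1 so that it counts the events the model is introduced for.

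The cost is wording in both documents and one small addition to the analysis programs. The event comparisons are already planned; the sparse-data method is new. No extra data or subjects are needed. The changes should be made before anyone choosing the analysis sees unblinded safety results.

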4.6.3. Safety summary of Phase 2 MS trial (MN-166-CL-001)

In a Phase 2 trial conducted in CEE in RRMS patients, subjects were treated with either placebo or MN-166, 30 or 60 mg/d up to two years. Enrolled subjects received study drug for 12 months in the “core period” and if eligible, continued to the “extension period” for an additional 12 months of treatment. A total of 297 subjects were enrolled, 103 subjects were randomized to placebo group, 95 subjects were randomized to the 30 mg/d group and 99 subjects were randomized to the 60 mg/d group. Two-year completion of the 60 mg/d group was 86%.

Core period (12 m) 1 st year	# of enrolled subject	Extension period (12 mo) 2 nd year	# of enrolled subjects

CONFIDENTIAL

	(N)		(N)
Placebo	103	P-30mg	49
		P-60mg	48

During the 12-month double-blind core-period, the adverse events most frequently reported (> 5%) occurred in the SOCs of Infections and Infestations (36%), Nervous System Disorders (19%), Gastrointestinal Disorders (15%), Psychiatric Disorders (13%), General Disorders and Administration Site Conditions (9%), and Musculoskeletal and Connective Tissue Disorders (7%). No significant differences in TEAEs by SOC were observed between treatment groups. There was a slight dose related increase in the percent of subjects with gastrointestinal AEs: 8%, 12%, and 15% for placebo, 30 mg/d, and 60 mg/d treatment groups, respectively.

During the core-period, more treatment-related TEAEs were experienced by subjects in the 60 mg/d group (26 TEAEs) compared to the 30 mg/d (18 TEAEs) or placebo group (12 TEAEs). The most common treatment-related AEs were headache (n =3) and nausea (n =2) in the 30 mg/d; nausea (n =4), headache (n =3), vomiting (n=2) and dizziness (n =2) in the 60 mg/d group; and upper respiratory infection (n =5) and headache (n =2) in the placebo group.

During the 12-month open-label extension period, five additional treatment-related TEAEs occurred. These TEAEs were night cramps (1 subject 60 mg/d), hepatotoxicity (1 subject 60 mg/d), depression (1 subject 60 mg/d), and pruritus (2 subjects in placebo to 60 mg/d).

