1. STUDY DESIGN

This is a multicenter, phase II, randomized, double-blind, placebo controlled, parallel group study designed to generate proof-of-concept evidence to evaluate the activity of Ibudilast (MN-166) on imaging measures of brain atrophy and tissue integrity, to evaluate the safety and tolerability of Ibudilast over two years, and to identify imaging markers for measuring biologic activities of potential therapies in progressive MS. A total of 250 male and female subjects from 21 to 65 years old, inclusive, will be enrolled into two treatment groups across sites within the NeuroNEXT network. Subjects will be randomized in a 1:1 fashion to receive either Ibudilast (100 mg/day; n = 125) or matching placebo (n = 125). Randomization of subjects will be stratified by disease status [primary progressive MS (PPMS) or secondary progressive MS (SPMS)] and immunomodulation therapy [untreated with long-term MS disease modifying therapy or receiving either glatiramer acetate (GA) or interferon beta (IFN β -1a: Avonex, Rebix or IFN β -1b: Betaseron, Etavia) treatment]. Study drug will be administered either two times per day (i.e., MN-166 50 mg or placebo taken in the morning and evening) or three times per day, depending on subject’s tolerance to study drug. The study will consist of a screening phase (up to 45 days), followed by a treatment phase (96 weeks), and a follow-up visit (1 month post week 96 visit). Thus, subjects will be involved for approximately 100 weeks in the various phases of the study.

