- Y_i represents the number of treatment related SAEs experienced by the i^{th} subject.
- T_i represents the number of months between the date of randomization and the date of last follow-up for the i^{th} subject.
- $x_{1i} = 1$ if i^{th} subject was thought to be receiving immunomodulation therapy at randomization (IFN/GA), and 0 if the subject was not thought to be receiving immunomodulation therapy
- $x_{2i} = 1$ if i^{th} subject was thought to have primary progressive MS at randomization, and 0 if the subject was thought to have secondary progressive MS
- $x_{3i} = 1$ if i^{th} subject was randomized to the Ibudilast group, and 0 if the subject was randomized to placebo group
- ϵ_i is random error for the i^{th} subject

To determine if the rate of treatment related SAEs differ across treatment group we will test the following hypothesis:

$$H_0: \beta_3 = 0 \text{ vs. } H_A: \beta_3 \neq 0$$

If the null hypothesis is rejected, the direction of β_3 will indicate the direction of the observed effect. Values of $\beta_3 > 0$ indicate an increased rate of treatment-related AEs associated with the Ibudilast group, while values of $\beta_3 < 0$ indicate a decreased rate of treatment-related AEs associated with the Ibudilast group.

Treatment-related SAEs will be analyzed in the same manner described above. Additional safety analyses will also assess all treatment-emergent AEs, treatment-emergent SAEs, unanticipated SAEs, and treatment-related & unanticipated SAEs in a similar manner.

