The analysis used the proposed time points of 0, 24, 48, 72, and 96 weeks. Power curves were computed for DS1, DS2, and for their average (Avg). Avg was based on averaging the LMM parameter estimates across the data sets (e.g., average slope = [DS1 slope + DS2 slope] / 2). Avg was an attempt to pool information from the two data sets without the raw data (the raw data for DS2 was unavailable). A 10% dropout rate was assumed and all estimated sample sizes were inflated by this percentage (i.e., final sample size = initial sample size \times 1.10). Given the resources required for obtaining and analyzing 3T scans, the type I error rate was set at $\alpha = 0.10$. Figure 7.1 shows power curves for the three smallest effect sizes (30%, 35%, and 40%). Focusing on Avg for the middle effect size (35%), the figure indicates that a single-arm $N / 2 = 125$ provides close to 80% (power = 0.80 is the horizontal dashed line). The middle effect size is important as it nearly corresponds to the upper effect size of the aforementioned Ibudilast study (effect size = 36%). The Avg data source is preferred because it approximates a pooling of the information from both samples. The feasibility of $N / 2 = 125$ as the single-arm sample size was examined by calculating power for effect sizes with $\alpha = 0.10$ for all three data sources (DS1, DS2, Avg). The power by effect size curve and data source is shown in Figure 7.2. The figure clearly shows that the study has adequate power across the range of possible values suggested by these two data sources. For the “best” data (DS1), our study has slightly less than 90% power to detect effects of approximately 40% or larger, and more than 90% power to detect effects on the upper end of the range of interest (50%). Most importantly, the figure shows that the power based on the Avg data source is very high for effects in the 33% - 36% range of greatest interest (approximately 80% - 85%). Therefore, based on these assumptions, we are confident that a per-arm sample size of $N / 2 = 125$ ($N = 250$ total participants) is sufficient to help ensure statistically reliable results for the proposed study.

Figure 9.1: Power as a Function of Single-arm sample size, effect size, and data set

[figure not shown]
[figure not shown]

Figure 9.2: Power as a Function of Effect Size and data source for sample size of 125 and alpha = 0.10

9.2. Primary Objective #2: Evaluate the safety and tolerability of Ibudilast (MN-166) versus placebo

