With an overall significance level of 0.10, the study will have 80% or greater power to detect differences in safety or tolerability of 15% or greater across the two groups. Thus, minor safety concerns may not be detected in this study – and would need to be assessed in a larger, future phase 3 trial. Nevertheless, the study is adequately powered to detect major safety concerns.

9.3. Major Secondary Objective (a): Evaluate the activity of Ibudilast (MN-166) versus placebo as measured by diffusion tensor imaging (DTI) in pyramidal white matter tracts.

The power analysis was based on longitudinal DTI pilot data with the outcome measure being longitudinal diffusivity (LD) within corticospinal tracts among RRMS and SPMS starting therapy with natalizumab (Fox 2010). Eighteen MS patients were measured five times over 24 months. Equation (2) was the basis for computing required sample size based on the LMM. In order to express power $(1 - \beta)$ as a function of the fixed sample size $(N / 2 = 125)$ and the other quantities, the following equation can be used

$$1 - \beta = \Phi \left[\left(\sqrt{\frac{125 \cdot \delta^2}{\left(\sum_k \sum_l^L \mathbf{X}_{kl}^T \mathbf{V}_{kl}^{-1} \mathbf{X}_{kl} \mathbf{P}_{kl} \right)_{4,4}^{-1}}} \right) - Z_{1-\alpha/2} \right]$$

where $\Phi[\cdot]$ is the cumulative distribution function of the standard normal distribution. Estimated power was calculated using Equation (3) for the δ effect sizes discussed previously. The results show that the estimated power was greater than 0.90 for the smallest effect size (30% difference in slopes). This result implies that $N = 250$ patients is sufficient to provide high power for testing the equality of LD slopes in the treatment and control groups for the range of plausible effect sizes that is anticipated in the proposed study.

9.4. Major Secondary Objective (b): Evaluate the activity of Ibudilast (MN-166) versus placebo as measured by magnetization transfer ratio (MTR) imaging in normal appearing brain tissue.

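### SAP 7.2.1 compares the arms on a preferred term only when its whole organ class differs at 0.10, so a harm confined to one term can go without a formal comparison.

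*Combined protocol and SAP*

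**What the plan says.** SAP 7.2.1 compares the percentage of subjects with any treatment-related AE by logistic regression, first overall and then within each MedDRA SOC. The next level down is conditional: "If there are significant differences between groups within any specific SOC, then additional tests will compare differences across groups for specific MedDRA preferred terms". The stated aim of that step is to look for the cause of a class difference already seen.

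The end of 7.2.1 widens the scope: "Additional safety analyses will also assess all treatment-emergent AEs, treatment-emergent SAEs, unanticipated SAEs" and further categories are to be handled in a similar way.

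The level comes from SAP section 6: "all analyses to address the primary and major secondary objectives will be conducted at the 0.10 significance level". Safety is Primary Objective #2. The tests are two-sided, since 7.2.1 also interprets the favourable direction: "we will conclude that Ibudilast was responsible for a significantly lower frequency of treatment-related AEs". No adjustment across classes or terms is stated.

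The only stated safety power is in SAP 9.2: "the study will have 80% or greater power to detect differences in safety or tolerability of 15% or greater across the two groups". None is given for SOC or preferred-term tests.

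Separately, the Safety Analysis paragraph of the protocol synopsis plans counts and percentages per arm by SOC and preferred term, with no condition attached. It plans no difference or interval at term level.

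**The concern.** Drug harms usually appear as specific events such as vomiting, depression or hepatotoxicity. A SOC collects many terms, most of them unrelated to any one mechanism. If only one term is raised, the other events in the class add subjects to both arms. They increase the variance of the class comparison and slightly shrink its difference. The class test is therefore weaker than the term test it controls, and increasingly so as the class gets busier.

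Followed as written, the rule makes the formal comparison of a term depend on that weaker test. This matters because safety is a primary objective and 100 mg/d had previously been given for far shorter periods than 96 weeks. The quarterly review described in SAP 10.3 also works by body system.

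**Working it through.** **1. The plan's own figure.** For two proportions with n per arm, power = Φ{[Δ − 1.645·√(2p̄(1−p̄)/n)] / √[(p₀(1−p₀)+p₁(1−p₁))/n]}. For 20% vs 35% and n = 125: (0.15 − 1.645 × 0.0565)/0.0557 = 1.03, so power is 85%. Other control rates give 93% (at 10%), 82% (25%), 79% (30%) and a minimum of 77% (42.5%). The stated 80% is therefore roughly right for a 15-point difference. It does not address single terms, where plausible differences are smaller.

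**2. Inputs for the gate.** From the documents: 125 per arm, two-sided 0.10. Term-level rates for this trial are not given, so 2% vs 8% is an assumption. The class rates are guided by protocol 4.6.3 (earlier 12-month MS trial):
- Treatment-related events: 12 on placebo in 103 subjects over all classes, hence at most 12/103 = 11.7% of subjects. The commonest terms were 5/103 = 4.9% and 2/103 = 1.9%. A class rate of 3%–5% is plausible.
- All treatment-emergent events: gastrointestinal 8% on placebo. Psychiatric 13%, gastrointestinal 15%, nervous system 19% and infections 36% are not given as placebo rates, so they serve only as a range for busy classes.

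**3. Dilution.** If the other terms affect a share b of subjects in both arms independently, the class rate is 1 − (1−p)(1−b). For a placebo class rate of 8%, b = 1 − 0.92/0.98 = 0.061. The active class rate is then 1 − 0.92 × 0.939 = 0.136.
- Term: 0.06/√(2 × 0.05 × 0.95/125) = 0.06/0.0276 = 2.18.
- Class: 0.056/√(2 × 0.108 × 0.892/125) = 0.056/0.0393 = 1.43.

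The critical value is 1.645. The expected term statistic exceeds it and the expected class statistic does not.

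**4. Simulation.** Expected term counts are small (2.5 vs 10), so the probabilities were simulated, with a pooled two-proportion test standing in for the logistic model. The direct term test is significant in 75% of trials. The last column is 1 − (both significant)/(term significant); at 8%, 1 − 0.394/0.752 = 48%.

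| Placebo class rate | Class test significant | Both significant | Term significant but not formally tested |
|---|---|---|---|
| 3% | 67% | 64% | 15% |
| 5% | 54% | 51% | 32% |
| 8% | 42% | 39% | 48% |
| 13% | 32% | 29% | 62% |
| 15% | 29% | 26% | 65% |
| 19% | 25% | 22% | 70% |
| 36% | 17% | 15% | 81% |

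**5. Sensitivity to the assumed effect** (b is the share of subjects with other terms).
- 1% vs 5%: direct 66%; gate opens 31% at b = 5% and 18% at b = 15%.
- 2% vs 10%: direct 89%; gate 63%, 38% and 22% at b = 5%, 15% and 36%.
- 5% vs 20%: direct 98%; gate 92% and 75% at b = 5% and 15%.

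**6. One data set.** A term at 10/125 vs 2/125 gives p = 0.018 (Fisher 0.034). If its class stands at 32 vs 27, the class p is 0.46 and the term is not tested. The risk difference would have been 8/125 = 6.4 points, 90% CI 6.4 ± 1.645 × 2.67, or 2.0 to 10.8.

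**The case against.** The strongest defence is that going from class to term is an ordinary way to limit false signals. Twenty independent null tests at 0.10 give 1 − 0.9²⁰ = 88% chance of at least one. This stands as an argument against bare term-level p-values, but not against estimates with intervals.

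There are other safeguards. The medical safety monitor reviews every SAE individually (SAP 2.2), and the protocol compares laboratory values between arms (12.1.2). These help with serious and hepatic harms, but not with a non-serious single term.

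Related terms can also rise together, as gastrointestinal ones may. If two independent terms each go from 2% to 8%, the gate opens in 82% of trials at an 8% class rate and 64% at 15%. This stands too: the loss applies to harms confined to one term.

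A reader might infer four stronger things that the documents do not support.
- *A non-significant class is taken as clearance.* No section says so. SAP 9.2 concedes that smaller harms may be missed, although 7.2.1 has no counterpart to the warning about non-rejection that 7.1 gives for BPF.
- *Untested terms are never seen by arm.* The synopsis tabulates them without condition.
- *Most single-term harms are lost.* That is so for small effects or busy classes. It is not so for 2% vs 8% at the 3%–5% class rates plausible for treatment-related events, which are the main analysis.
- *The earlier trial shows the dilution.* Protocol 4.6.3 reports "No significant differences in TEAEs by SOC were observed between treatment groups" beside gastrointestinal rates of 8%, 12% and 15% by dose. That is a gradient at class level, so it does not show one term hidden inside a class. The protocol's safety overview (4.6.2) still discusses nausea and vomiting by dose.

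**Conclusion.** The point holds as a loss of formal term-level comparison. For a term rising from 2% to 8%, the rule would leave untested about 15%–32% of significant term differences at class rates of 3%–5%, 48% at 8%, and 62%–81% at 13%–36%. These figures assume 125 per arm, two-sided 0.10, independence of the term from the rest of its class, and no effect on the other terms. The effect size and class rates are assumptions informed by the earlier trial. Extending the gate to all treatment-emergent events rests on the SAP's wording that these are handled similarly.

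This is a worthwhile, inexpensive improvement to the safety analysis. It does not put the trial's safety conclusions in doubt by itself.

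**What to change.** Remove the SOC-significance condition from 7.2.1. For every preferred term above a minimum count (for example, at least 4 subjects in either arm), add the risk difference and 90% CI to the planned n (%) table. Do this for treatment-related and for all treatment-emergent AEs, labelled as descriptive and unadjusted for multiplicity. Keep the SOC tests as a summary, and add one sentence saying that a non-significant SOC result is not evidence of no harm.

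The cost is two extra columns from data already collected. The downside is more intervals to read, some of which will exclude zero by chance. The descriptive label and the absence of a bare p < 0.10 flag keep that in proportion.
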